11.18 Sample Shipment

All laboratory testing samples are to be shipped overnight in designated temperature conditions to the central laboratory where samples will be analyzed.

All frozen serum and nasal fluid for biomarkers are to be shipped monthly on dry ice to the central laboratory. Shipments should be made only on Mondays and Tuesdays to ensure receipt of the specimens by Friday.

12 SAFETY ASSESSMENTS

12.1 Compliance

Participants will be asked to bring study medication with them to selected scheduled visits (Visits 2 and 3 during Part 1; Visits 3 and 4 during Part 2). Study sites will be provided with a scale and weight of the study medication will be obtained before the first use (at Visit 2 during Part 1; at Visit 3 during Part 2) and at each visit after use (Visit 3 during Part 1; Visit 4 during Part 2).

At Baseline, study personnel will be asked to take out study medication bottle from the carton, weigh the bottle and record the weight. At each subsequent visit, study personnel will need to weigh the bottle without the carton and record weight. This procedure should be followed every time study medication is dispensed and returned. Sites will be provided scales, which will be calibrated prior to each use. Weight will be recorded in grams. Study personnel will be instructed to record measurements into the eCRF.

12.2 Safety Monitoring

Local and systemic adverse events (AEs) related to intranasal route of administration during 14 days of treatment and 28 days of follow-up (7 and 28 days after the last dose of the study) will be recorded for the safety phase of the study in healthy volunteers (Part 1). Additionally, local and systemic AEs will be recorded in subjects with a history of seasonal allergic rhinitis during the efficacy phase of the trial (Part 2).

Safety monitoring will include infectious complications related to B244 (by symptoms and/or testing; pulmonary, nasal, neurological), local and systemic AEs related to intranasal route during treatment and at follow-up. Local AEs include runny nose, nasal congestion, sneezing, nasal itching, palate itching, anosmia, nasal ulceration, nasal bleeding, sore throat, cough, Bell's palsy, other neurologic complications, fevers, chills, headache, muscle aches, decreased appetite, nausea, vomiting, and rash.

Sponsor will distinguish between immediate (onset of reaction is during the first 30 minutes after administration) and delayed (onset of action is after the first 30 minutes of administration) effects for safety reporting of adverse events.

Due to the nature of the nasal allergen challenge (in Part 2 of the study) which consists of delivering allergen directly into the airways of an allergic individual, a medical doctor trained for treating anaphylaxis must be present within the building. A crash cart and the crash team telephone number must be readily available. The nasal allergen challenge involves spraying a solution with very small amounts of ragweed antigen (allergy causing substance) into the nose. The side effects of this can be nasal blockage, excessive nasal discharge (similar to seasonal allergy symptoms), which may be delayed by several hours. There is also a risk of bronchoconstriction (wheezing), especially if one has a history of asthma. The most serious risk of having a nasal challenge test is anaphylactic reaction. This reaction is a medical emergency, causing difficulty breathing and a dangerously low blood pressure. However, anaphylactic reactions with nasal challenge test are rare and the physician will be monitoring subjects closely after the challenge during the time they are in clinic. If subjects notice symptoms noted above after they have left the clinic, they should call 911 immediately.

A 180 day follow up contact for collecting serious adverse events and new onset medical conditions for Part 1 will be the medical monitor described in section 15.7 ([name], [name]; [contact]; or [name], [contact]; [contact]). Alternatively, the site will contact subjects 180 days after the last visit and after study close out to collect SAEs or new onset medical conditions.

12.3 Pregnancy Reporting

Any pregnancy will be reported by study participants during their study participation.

Participants who report pregnancy or lactation during the review of inclusion/exclusion criteria prior to randomization will not be enrolled in the trial. In case of pregnancy, Investigational Product should be discontinued and the Sponsor informed. Follow-up of the pregnancy will be mandatory until the outcome is available.

12.4 Study Completion

A completed participant is one who has completed all study visits. Day 42 study visit is defined as the participant's last visit (Visit 5) for Part 1, while Day 28 study visit is defined as the participant's last visit (Visit 4) for Part 2.

12.5 Internal Safety Committee

An internal safety committee meeting will review the 2 week treatment safety data during Part 1 phase of the study and, if there are no safety concerns, will proceed to Part 2 of the study to evaluate preliminary efficacy in subjects with a history of seasonal allergic rhinitis (SAR).

12.6 Subject Withdrawal Criteria

A subject may withdraw from the study at any time at his/her own request, or may be withdrawn at any time at the discretion of the Investigator for safety, behavioral, or administrative reasons.

Reasons for withdrawal (subjects who refuse to return for any remaining study visits) or discontinuation (subjects who prematurely stop the application) at any time during the study may include, but are not limited, to the following:

For safety reasons, either at the discretion of the Investigator or at the subject's request

For protocol violations at the discretion of AOBiome

Due to concomitant therapy that could interfere with the results of the study (the Investigator will report all such information on the CRFs and decide, in accordance with AOBiome, whether the subject is to be withdrawn).

All premature discontinuations and their causes must be carefully documented by the Investigator on the CRF or if needed on the AE form.

If, for any reason, a subject is withdrawn before completing the final visit, the reason for termination will be entered on the CRF. All data gathered on the subject prior to termination will be made available to AOBiome. Subjects not completing the entire study should be fully evaluated when possible. The appropriate CRFs should be completed.

If the subject chooses to withdraw before completing the study, the subject should notify the study coordinator who will instruct the subject on completion of assessments for Unanticipated

visit (Appendix A). For subjects who refuse to complete the assessments for their early termination, every attempt must be made to check on their status, using any mode of communication such as telephone, email, fax, or text.

13 EFFICACY ASSESSMENTS

Efficacy endpoints will be descriptively summarized and will include the number of observations, mean, median, standard deviation, minimum, and maximum of scores/values at all applicable time points and for all treatments in the ITT Population.

For Part 2 phase of the study, the following secondary efficacy assessments will be obtained:

- Change in TNSS from baseline to 14 days of prophylaxis treatment.
- Change in subjective nasal symptom scores of nasal congestion, rhinorrhea, nasal itching, and sneezing from baseline to 14 days of prophylaxis treatment.
- Nasal symptom-free response rate within each individual symptom scores and percentage of subjects with a 25% or 50% reduction in TNSS after 14 days of prophylaxis treatment.

The following exploratory efficacy assessments will be obtained:

- Change in Peak Nasal Inspiratory Flow (PNIF), nasal inflammation score using otoscope, intranasal nitric oxide levels, and cytokine concentration in nasal cavity and blood from baseline to 14 days of B244 application and during prophylaxis treatment setting.

Fisher's exact test will be used for efficacy parameters that report frequencies or incidence of measured events to make treatment group comparisons. For the continuous endpoints a one-sided two-sample equal-variance z-test will be used to compare treatment group means.

14 STATISTICAL CONSIDERATIONS

14.1 Sample Size

Part 1 (safety and tolerability evaluation in healthy volunteers) will enroll 24 subjects. Up to 12 subjects per dose cohort (n=8 active, n=4 vehicle) will be enrolled, with a target of 20 subjects completed (10 subjects per dose cohort; n=7 active, n=3 vehicle) assuming a 16.7% drop out rate. The two dose cohorts are 1×10^9 cells/ml and 4×10^9 cells/ml.

Part 2 (preliminary efficacy evaluation in subjects with a history of SAR to ragweed pollen) will enroll 42 subjects. Up to 14 subjects per arm (1×10^9 cells/ml; 4×10^9 cells/ml or vehicle) will be enrolled, with a target of 12 subjects per arm for a total of 36 subjects completed, assuming a 10-15% drop-out rate.

14.2 Populations for Analysis

ITT: includes all randomized participants.

Safety: includes all subjects who received at least 1 dose of study medication.

Per Protocol: subjects who administered at least 50 % of IP, have at least one baseline and post baseline in clinic visit and did not have any major protocol violations.

14.3.1 Disposition

A tabulation of the disposition of subjects will be presented, including the number enrolled, the number randomized, the number treated, and the reasons for study discontinuation will be reported. Summaries of the number in each analysis set will be summarized. Entry criteria and protocol deviations will be listed.

14.3.2 Demographic and Baseline

Demographic and baseline characteristic data summarization will be performed in order to descriptively assess the comparability of strata and treatments. Data to be tabulated will include age, race, ethnicity, height, weight, and BMI, as well as baseline characteristics related to medical history.

14.4 Safety Analyses

14.4.1 Definitions

All adverse events recorded during the study will be coded according to Medical Dictionary for Regulatory Activities.

The primary analysis of safety will be based on the safety population, which is defined as all subjects receiving at least 1 dose of B244 or placebo. Adverse events (AEs) will be coded using the Medical Dictionary for Regulatory Activities (MedDRA®) for purposes of summarization. All AEs occurring during the study will be included in by-subject data listings and tabulated. Events leading to death, SAEs, and events resulting in study discontinuation will be summarized using standard descriptive statistics, and presented by treatment arm. Exposure to study drug and reasons for discontinuation of study treatment will be tabulated. Shift tables relative to the normal range will be provided for laboratory parameters. Additional analyses will be performed, if warranted, upon review of the data.

14.4.2 Adverse Events

All adverse events (AEs) recorded during the study through the date of randomization through 28 days after the last dose of study drug will be analyzed.

All AE's will be coded according to Medical Dictionary for Regulatory Activities and summarized using System Organ Class (SOC) and Preferred Term (PT).

AE's will be summarized using incidence rates. Therefore, each subject will only contribute once for a given adverse event SOC or PT.

A summary of the incidence of any adverse event, SAE, and adverse events leading to discontinuation will be presented. Summaries will display, by strata and treatment sequence, the incidence of patients with events, the frequency of patients with events within each primary system organ class and by preferred terms. For each preferred term and each system organ class a patient will be counted only once. For summaries on severe or drug-related AE, for a given patient, the highest severity or relationship for a specific preferred term will be considered.

14.4.3 Deaths and Serious Adverse Events

Serious adverse events and events leading to death will be summarized overall and by primary system organ class and preferred term.

14.4.4 Adverse Events Leading to Treatment Discontinuation

Adverse events leading to treatment discontinuation will be summarized overall and by primary system organ class and preferred term.

14.5 Efficacy Analyses

Additional exploratory analyses will be defined in the Statistical Analysis Plan.

14.5.1 Handling of Dropouts or Missing Data

Missing data will not be imputed for analysis.

Subjects who dropout after enrollment but prior to randomization will be replaced.

14.6 Clinical Trial Protocol Deviations

All the following deviations will be summarized on the all randomized patient population:

- Inclusion or exclusion criteria not satisfied.
- Deviations related to the Investigational Product administration
- Not permitted concomitant medications.

15 ADVERSE EVENTS (AE) AND SERIOUS ADVERSE EVENTS (SAE)

The Investigator and study staff are responsible for detecting and recording AEs and SAEs during scheduled safety evaluations and whenever such information is brought to their attention. This section of the protocol provides definitions and detailed procedures to be followed.

15.1 Definition of an AE

An AE is any untoward medical occurrence in a study participant which is temporally associated with the use of a medicinal product, regardless of its potential relationship to the medicinal product. An AE, therefore, can be any unfavorable or unintended sign, including an abnormal symptom, or disease (new or exacerbated), whether or not related to the investigational product (IP).

Examples of an AE include:

Exacerbation of a pre-existing condition including either an increase in frequency and/or intensity of the condition.

New conditions detected or diagnosed after investigational product administration even though it may have been present prior to the start of the study.

Signs, symptoms of a drug interaction.

Signs, symptoms of a suspected overdose of either investigational product or a concurrent medication (overdose per se should not be reported as an AE/SAE).

AEs may include pre- or post-treatment events that occur as a result of protocol-mandated procedures (i.e., modification of participant's previous therapeutic regimen).

15.2 Definition of a SAE

A serious adverse event is any untoward medical occurrence that, at any dose:

- (a) results in death.
- (b) is life-threatening.

NOTE: The term 'life-threatening' in the definition of 'serious' refers to an event in which the participant was at risk of death at the time of the event. It does not refer to an event, which hypothetically might have caused death, if it were more severe.

- (c) requires hospitalization or prolongation of existing hospitalization.

NOTE: In general, hospitalization signifies that the participant has been detained (usually involving at least an overnight stay) at the hospital or emergency ward for observation and/or treatment that would not have been appropriate in the physician's office or out-patient setting. Complications that occur during hospitalization are AEs. If a complication prolongs hospitalization or fulfills any other serious criteria, the event is serious. When in doubt as to whether "hospitalization" occurred or was necessary, the AE should be considered serious. Routine hospitalizations or elective surgeries are generally not regarded as SAEs.

- (d) results in disability/incapacity, or

NOTE: The term disability means a substantial disruption of a person's ability to conduct normal life functions. This definition is not intended to include experiences of relatively minor medical significance such as uncomplicated headache, nausea, vomiting, diarrhea, influenza, and accidental trauma (e.g. sprained ankle) which may interfere or prevent everyday life functions but do not constitute a substantial disruption.

- (e) is a congenital anomaly/birth defect

- (f) Medical or scientific judgment should be exercised in deciding whether reporting is appropriate in other situations, such as important medical events that may not be immediately life-threatening or result in death or hospitalization but may jeopardize the participant or may require medical or surgical intervention to prevent one of the other outcomes listed in the above definition. These should also be considered serious. Examples of such events are invasive or malignant cancers, intensive treatment in an emergency room or at home for allergic bronchospasm, blood dyscrasias or convulsions that do not result in hospitalization, or development of drug dependency or drug abuse.

15.3 Time Period, Frequency, and Method of Detecting AEs and SAEs

All AEs occurring after administration of the first dose of study medication and on or before the final assessment must be reported as AEs. All AEs must be recorded irrespective of whether they are considered drug-related.

At each assessment in the period defined above, AEs will be evaluated by the Investigator and recorded.

Any AEs already documented at a previous assessment and designated as ongoing, should be reviewed at subsequent assessments as necessary. If these have resolved, this should be documented. Changes in intensity or frequency of AEs should be recorded as separate events (i.e., a new record started).

The recording of AEs and SAEs are described in Section 14.4 (“Recording of AEs and SAEs”).

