15.4 Recording of AEs and SAEs

All clinical events, including either observed or volunteered problems, complaints or symptoms are to be recorded on the Adverse Events page(s) of the CRF. The need to capture this information is not dependent upon whether the clinical event is associated with study treatment. Adverse clinical events resulting from concurrent illnesses or reactions to concurrent medications are also to be recorded. In order to avoid vague, ambiguous, or colloquial expressions, the AE should be recorded in standard medical terminology rather than the participant’s own words.

Each adverse clinical event is to be evaluated for duration, intensity, and whether the event may be associated with the investigational product (IP) or other causes. Start and stop dates, relationship to investigational product (IP), medical management, and alternative causality of event must be recorded in the Adverse Events section of the CRF. AEs believed to be possibly related to investigational product (IP) must be followed until resolution.

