### **2.4.1. Adverse Events / Serious Adverse Events**

Adverse events will be coded using the medical dictionary of regulatory activities (MedDRA Version 20.1) dictionary.

Treatment-emergent adverse events (TEAEs) will be defined as any AE that starts on or after the first administration of study medication. Any event that started prior to the first administration of study medication but worsened in severity after the first administration will be recorded as a new event so that it may be captured as a TEAE. AEs with an unknown onset date will be counted as treatment-emergent unless the event resolved prior to the first administration. Section 2.8 describes the imputation rules for partial dates.

Treatment-emergent adverse events that are documented as occurring within 30 minutes after any of the doses will be summarized with the other TEAEs and separately from the other TEAEs.

The incidence of TEAEs will be presented by system organ class (SOC) and preferred term (PT). Events will also be summarized by severity and relationship. The incidence of TEAEs leading to withdrawal from the study and SAEs, including deaths, will be presented in both summary tables and data listings.

All AEs will be presented in data listings.

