14.3.1.3-2	Summary of Treatment Emergent Adverse Events by Body System, Preferred Term and Severity – Safety Population - Part 2
14.3.1.4-1	Summary of Treatment Emergent Adverse Events by Body System, Preferred Term and Relationship to Study Medication – Safety Population - Part 1
14.3.1.4-2	Summary of Treatment Emergent Adverse Events by Body System, Preferred Term and Relationship to Study Medication – Safety Population - Part 2
14.3.1.5-1	Summary of Immediate Treatment Emergent Adverse Events by Body System and Preferred Term – Safety Population - Part 1
14.3.1.5-2	Summary of Immediate Treatment Emergent Adverse Events by Body System and Preferred Term – Safety Population - Part 2
14.3.1.6-1	Summary of Delayed Treatment Emergent Adverse Events by Body System and Preferred Term – Safety Population - Part 1
14.3.1.6-2	Summary of Delayed Treatment Emergent Adverse Events by Body System and Preferred Term – Safety Population - Part 2
14.3.1.7-1	Summary of Adverse Events Leading to Study Discontinuation – Safety Population - Part 1
14.3.1.7-2	Summary of Adverse Events Leading to Study Discontinuation – Safety Population - Part 2
14.3.1.8-1	Summary of Serious Adverse Events – Safety Population - Part 1
14.3.1.8-2	Summary of Serious Adverse Events – Safety Population - Part 2
14.3.2.1-1	Summary of Laboratory Evaluations – Hematology – Safety Population - Part 1

Table Number	Table Title
14.3.2.1-2	Summary of Laboratory Evaluations – Hematology – Safety Population - Part 2
14.3.2.2-1	Summary of Laboratory Evaluations – Chemistry – Safety Population - Part 1
14.3.2.2-2	Summary of Laboratory Evaluations – Chemistry – Safety Population - Part 2
14.3.2.3-1	Summary of Laboratory Evaluations – Urinalysis – Safety Population - Part 1
14.3.2.3-2	Summary of Laboratory Evaluations – Urinalysis – Safety Population - Part 2
14.3.2.4-1	Summary of Laboratory Evaluations – Other – Safety Population - Part 1
14.3.2.4-2	Summary of Laboratory Evaluations – Other – Safety Population - Part 2
14.3.3-1	Summary of Vital Signs – Safety Population - Part 1
14.3.3-2	Summary of Vital Signs – Safety Population - Part 2
14.3.4-1	Summary of Electrocardiograms – Safety Population - Part 1
14.3.5-1	Summary of Ambulatory Blood Pressure Monitoring – Safety Population - Part 1

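### Protocol 15.3 opens a new AE record at any change in intensity, including easing, while the SAP intends only worsening to make a pre-dose event treatment-emergent; as written, an easing pre-dose event becomes a TEAE

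*Protocol*

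**What the plan says.** Protocol section 15.3 deals with AEs that are already documented and ongoing when they are reviewed at a later assessment. It ends with this rule: "Changes in intensity or frequency of AEs should be recorded as separate events (i.e., a new record started". It does not limit the rule to worsening. Section 15.4 lists what each AE entry carries: "Start and stop dates, relationship to investigational product (IP), medical management, and alternative causality of event must be recorded".

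SAP section 2.4.1 gives the general definition: "Treatment-emergent adverse events (TEAEs) will be defined as any AE that starts on or after the first administration of study medication". For an event that began before dosing, the next sentence provides that one which "worsened in severity after the first administration will be recorded as a new event so that it may be captured as a TEAE". Worsening is the only trigger it names.

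On timing, protocol section 12.2 separates "immediate (onset of reaction is during the first 30 minutes after administration) and delayed (onset of action is after the first 30 minutes of administration". SAP 2.4.1 says that TEAEs "documented as occurring within 30 minutes after any of the doses will be summarized with the other TEAEs and separately from the other TEAEs". SAP section 4.1 then lists, for each part, an immediate table (14.3.1.5) and a table titled "Summary of Delayed Treatment Emergent Adverse Events by Body System and Preferred Term" (14.3.1.6).

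Neither document has a rule that links the successive records of one event, or that sets aside a record opened because the event eased.

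**The concern.** The SAP relies on re-recording as the signal that a pre-existing event got worse. The protocol sends the same signal when the event gets better. A programmer who applies the TEAE definition to each record's start cannot tell the two apart, so a subject whose pre-dose complaint improved on treatment is counted with a treatment-emergent event.

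AEs are one component of the Part 1 primary endpoint, with physical examination and vital signs, and part of a secondary endpoint in Part 2. The arms are small, so one misclassified subject visibly shifts a percentage. The immediate/delayed split is a named safety output for an intranasal product, and the same missing link between records leaves it open which table a continuation record belongs to.

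**Working it through.** The plan gives no figure to reproduce. The check applies the written rules to hypothetical AE histories and then works out the weight of one subject.

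**Can a pre-dose AE exist?** Yes. The visit lists in protocol 10.5 and 10.6 include safety AEs at screening in both parts. In Part 2 they also include them at NAC titration and at the NAC #1 visit, where the challenge comes before the first dose. Section 15.1 allows that procedures required by the protocol may cause AEs before treatment. SAP 2.4.1 itself provides for events that started before the first dose. Whether challenge symptoms are to be recorded as AEs is not stated.

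**Rules applied.** TEAE: record start at or after first dose. Immediate: start 0 to 30 minutes after a dose. Delayed: start after 30 minutes. Each history is run twice: with a new record at any change, and with a new record on worsening only.

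| Hypothetical history (minutes from dose) | New record at any change | New record on worsening only |
|---|---|---|
| A. Pre-dose moderate, eases to mild at +60 | TEAE | Not a TEAE |
| B. Pre-dose mild, worsens at +60 | TEAE | TEAE |
| C. Reaction at +10, eases at +45 | Immediate; also delayed if the new record's onset is used | Immediate only |
| D. Reaction at +10, eases at +20 | Immediate only | Immediate only |
| E. Reaction at +60, eases at +120 | Delayed only | Delayed only |

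A and B show the conflict. The any-change rule gives both the same status, although the SAP's worsening sentence is there to separate them. C is conditional: it needs the easing to be entered as its own record and the split to be made from that record's onset. D and E show where no harm arises.

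**Does counting each subject once help?** Protocol 14.4.2 counts a subject once per system organ class or preferred term. In A the subject has no other record of that term after dosing, so there is no duplicate to remove and the false entry stays. In C the two entries would sit in different tables, so the rule does not act on them.

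**Weight of one subject.**
- Part 1: 8 active per dose cohort; vehicle 4 + 4 = 8. One subject = 1/8 = 12.5 percentage points.
- Part 2: 14 per arm. One subject = 1/14 = 7.1 percentage points.

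These use planned enrolment (SAP 2.7), on the assumption that all enrolled subjects are dosed and so enter the safety population.

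**The case against.** **The rule in 15.3 works from visit to visit.** Its paragraph concerns AEs documented at a previous assessment and still ongoing. Congestion that comes and eases within the hour of on-site observation need not produce two records. This stands, and it removes most of the force from the immediate/delayed examples. It does not help the TEAE problem: an AE documented at screening or titration and found milder at a later visit is exactly what that paragraph covers.

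**The 30-minute split may not use record starts at all.** Section 15.4 names dates without times, the protocol speaks of the onset of the reaction, and the SAP speaks of events documented as occurring within 30 minutes. Section 11.17 makes the distinction under the study diary. The original onset may well govern. This stands as far as it goes, but neither document says so.

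**Easing pre-dose events are outside 15.3, or the SAP's specific sentence overrides the general one.** Section 15.3 requires reporting from first dose onward, and 15.1 gives exacerbation as its example for a pre-existing condition. Some investigators would therefore open no record. But pre-dose AEs are collected, the change happens after dosing, and the SAP sentence adds a route into TEAE status without excluding a record that already meets the general definition. The SAP's intent is clear; its rule does not carry it out.

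**AE summaries are descriptive and everything is listed.** True: no test of AE incidence is planned, and consecutive records would be visible in the listings for 24 and 42 subjects. That limits the harm without correcting the tables.

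A reader might go further and infer that easing immediate reactions will regularly appear as delayed ones, inflating the delayed table most in the arm with most immediate reactions; for instance, 3 of 8 subjects reading as 37.5%. The documents do not support that. The mechanism is only one possible reading, and no count of affected subjects has a source.

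**Conclusion.** The conflict between the two rules is real and gives a result that the SAP does not intend: a pre-dose AE that eases after first dose becomes a TEAE, and counting once per term does not remove it. This assumes that the site follows 15.3 literally and that the programmer applies the TEAE definition record by record. Part 2 is the more exposed if symptoms from NAC #1 are recorded as AEs, since they precede the first dose and would be expected to ease afterwards.

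For the immediate/delayed tables the finding is narrower. The documents leave open whether the original onset or the new record's onset governs, and a double entry follows only under the second reading, when easing occurs after 30 minutes and is recorded separately.

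The size is 12.5 points per affected subject in a Part 1 arm and 7.1 in a Part 2 arm. How many subjects would be affected is unknown. The matter should be settled before the tables are programmed, chiefly because it is cheap to settle.

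**What to change.** **Protocol 15.3.** Either limit the new-record rule to worsening, or keep it as it is and add a CRF field giving the number of the AE that the record continues. Say whether a rise in frequency alone counts as worsening: 15.1 treats it as an exacerbation, while the SAP sentence speaks only of severity.

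**SAP 2.4.1.** Add two statements:
1. A continuation record is a TEAE only if the parent event began on or after first dose, or if the post-dose severity exceeds the worst pre-dose severity.
2. Immediate or delayed status is taken from the onset of the parent event.

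The second statement is needed even if 15.3 is limited to worsening, because an immediate reaction that worsens after 30 minutes would still open a new record.

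**Linking.** Link records only through the recorded parent AE number or by data-management confirmation. Do not link by matching adjacent dates: with twice-daily dosing and dates without times, that could merge separate reactions to successive doses and hide a true delayed reaction.

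**Cost.** A sentence in the protocol or one CRF field, a short SAP paragraph, and a linking step in the AE dataset. A few records will need data-management review to confirm that they belong to one event.
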